Each of these objectives will be considered for time periods before and during the different waves of the COVID-19 pandemic. The cancer service provision during the first wave of COVID-19 in England (1st February 2020 to 30 June 2020) is likely to reflect the immediate response to the pandemic. By contrast, service provision during the subsequent waves of COVID-19 may provide more useful context for other settings when the NHS and care sectors are under prolonged pressures. Hence the analytical models and the interpretation of the results will reflect how relevant the context is to future decision-making. The overall findings across the four objectives will be synthesised and discussed with stakeholders who will help ensure the study provides information that is broadly accessible to service providers, and patients including those from underserved communities.

5. Research Plan / Methods

This study will use linked National Cancer Registration and Analysis Service (NCRAS) data which includes all cancer patients diagnosed in England (55), and links data from the Cancer Registry, Systemic Anti-Cancer Therapy (SACT) data, Radiotherapy Dataset (RTDS), Hospital Episodes Statistics (HES), and Cancer Waiting times data (Table 1). The research

design, proposed analyses and interpretation draws on insights from three tumour-specific clinical panels, and interviews with patients, through four interlinked WP.

WP 1: influence of patient and organisational factors on curative RT, surgical or noncurative strategies

(leads [name], [name])

Overview

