WP2 will build directly from the descriptive analyses in *WP1*, to assess inequalities in the receipt of curative versus non-curative treatments. The WP will consider these inequalities for time periods before the COVID-19 pandemic. We will then consider the impact of time periods during the pandemic on these inequalities. This WP will use insights from the clinical and PPIE panels with respect to the important organisational factors and equity subgroups to consider.

WP 2.1 Factors and comparators of interest for assessing inequalities

We will extract information from the linked data on patient characteristics including: age, sex, ethnicity, index of multiple deprivation (IMD) (quintiles), number and types of comorbidities, frailty level (60), date of primary cancer diagnosis, NHS trust hospital in which the patient is diagnosed, whether that NHS trust is a surgical and radiotherapy centre, patient's travel time to the nearest centre providing each curative intervention, the respective cancer alliance, and place of residence, including NHS region. The Charlson comorbidity index (61), the Cambridge Multimorbidity Score (62) and secondary care administrative records frailty (SCARF) index scores will be defined from HES diagnosis data (60).

We will identify surgical procedures and RT regimens with curative intent (56), and noncurative interventions, from the linked data. The definition of a 'curative intervention' strategy will require that either curative RT or surgery is received within six months of the diagnosis date. For RT to be defined as 'with curative intent' the dose and fractionation must also meet the criteria specified by guidelines for the time period in question. We will describe the variation in time to receiving either curative intervention, overall and across sociodemographic subgroups.

All interventions that do not meet the 'curative intent' criteria will be categorised as 'non-curative' interventions

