We will define those patients diagnosed in the 'post COVID-19 period' as from the start of the first national lockdown in England (March 11th 2020), and those in the preceding period as 'pre-COVID-19'. We will calculate the proportions of patients who received either 'curative intervention' for periods before and after the onset of COVID-19. The interpretation of the results will consider the specific time-period and context; for example, recognising that the provision of cancer services may reflect different organisational factors and pressures, such as those arising from the COVID-19 pandemic.

WP 2.2 Analysis

We will describe baseline characteristics of the study populations during the 'pre COVID-19' and 'COVID-19' periods, overall, and stratified by sociodemographic characteristics. We will report the total numbers of patients per quarter with each early-stage tumour during the 'pre' and 'COVID-19' periods, and the proportions who had curative RT and surgical treatments. We will report these proportions overall, and according to sociodemographic characteristics (e.g. age, sex, deprivation, ethnicity). We will address missing data with multiple imputation approaches, apart from for missing ethnicity data, for which we will define an 'unknown' category recognising that these data may be 'missing not at random'.

We will develop mixed-effect multivariable, multinomial logistic regression models to assess first, the proportions receiving curative RT and surgical strategies versus no curative intervention according to sociodemographic characteristics prior to COVID-19. Second, we will assess whether these inequalities changed during COVID-19 compared to previous periods.

Each model will adjust for other patient characteristics (e.g., comorbidity, frailty levels, performance status and cancer stage, distance to centre), time period, seasonality and allow for clustering within NHS trust hospitals and cancer alliances (random effects). In sensitivity analyses we will assess the robustness of results to, alternative standpoints, for example alternative approaches to handling the missing data, and exclusion of the first wave of COVID-19 (1st February to 30 June 2020) given the atypical nature of the care provided during this period.

WP 2.3 Outputs

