Sensitivity analyses will be undertaken to assess whether the results are robust to alternative definitions and assumptions. First, alternative inclusion criteria with respect to the time to curative treatment will be applied, including stricter (within three months of diagnosis), and looser (within nine month) cut-offs. Second, we will consider as an alternative instrumental variable, the percentage of eligible patients receiving RT versus surgery in each NHS trust in the year preceding the individual patient's diagnosis. Third, rather than using an instrumental variable analysis, the study will instead undertake conventional risk adjustment assuming that all relevant confounders have been measured, while assessing the impact of plausible levels of unobserved confounding on the results. Fourth, as in WP2, we will exclude data from the first wave of COVID-19 in England to assess the extent to which the results are sensitive to the inclusion of this period that is anticipated to be atypical for the provision of cancer services.

WP 3.5 Output and Interpretation of results (leads [name], [name], [name], [name], [name], [name])

We will report the relative effectiveness of RT versus surgery according to differences in absolute risk of 3-year mortality for each cancer. In interpreting the results, we will draw on insights from the clinical panels, and patient interviews, about the influence of local organisational factors and patient preferences on curative treatment decisions. The interpretation of the results will be according to the specific time-period. This will be important to provide recommendations for periods when the NHS is under exceptional pressures, such as during the first wave of COVID-19, and under prolonged pressures; for example, the increasing waiting lists for cancer care during the subsequent waves of COVID-19.

WP 4: Cost-effectiveness (Objective 4) (lead [name] and [name] advisor on combining inequality and costeffectiveness)

The cost-effectiveness analyses (CEA) will take the NHS and Personal Social Services perspective recommended by NICE. For each early-stage cancer we will report the relative cost-effectiveness of curative RT versus surgery strategies, over a lifetime time horizon. The choice of comparators will not include a 'no curative treatment alternative' as this is not a recommended treatment alternative for people with these early-stage cancers. The study will

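### WP2's COVID contrast has two start dates, a pre-COVID reference whose treatment windows run into the pandemic, and no stated calendar trend, so secular change may be reported as a COVID effect

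*Protocol*

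**What the plan says.** All references are to the protocol.

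- **Main cut (WP 2.1).** Patients are grouped by diagnosis date. The post-COVID group is defined "as from the start of the first national lockdown in England (March 11th 2020), and those in the preceding period as" pre-COVID.
- **First wave (Section 4, Aims and objectives).** The text refers to the "first wave of COVID-19 in England (1st February 2020 to 30 June 2020").
- **Sensitivity analysis (WP 2.2).** It lists "exclusion of the first wave of COVID-19 (1st February to 30 June 2020) given the atypical nature of the care provided" in that period. WP 3.4 carries the exclusion over: "Fourth, as in WP2, we will exclude data from the first wave of COVID-19 in England".
- **Outcome (WP 2.1).** A curative strategy "will require that either curative RT or surgery is received within six months of the diagnosis date". Everything else is classed as non-curative.
- **Model (WP 2.2).** Mixed-effects multinomial models adjust for patient factors such as "distance to centre), time period, seasonality and allow for clustering within NHS trust hospitals" and cancer alliances. No calendar trend, and no trend by sociodemographic group, is named.
- **Reporting (WP 2.3, Section 6.1).** The result is presented as the impact of COVID against pre-COVID periods, overall and by sociodemographic group, and is to have its own paper.

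**The concern.** Three features bear on one headline estimate.

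1. The protocol gives two dates for the onset of the pandemic, so some patients count as unaffected in one place and as first-wave patients in another.
2. Period is fixed at diagnosis, but the outcome accrues over the next six months. Some patients in the pre-COVID reference were therefore exposed to pandemic services when their treatment was decided or given.
3. The comparison spans 2015 to 2022 (2012 to 2022 for MIBC). A plain before/after term over so long a span absorbs any steady change in the use of RT or surgery. For the inequality question, it absorbs any trend that differs between sociodemographic groups.

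The protocol itself gives reasons to expect such change. Section 3.2 suggests that growing pathway complexity may widen inequalities. WP 1.2 expects the centralisation of services to differ over time. WP 2.1 judges curative RT by the guideline criteria of the period concerned. If trend and pandemic are not separated, a gap that was already widening could be reported as caused by COVID, or a narrowing one could hide a COVID effect.

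**Working it through.** The protocol gives no power or effect figure for this contrast, so there is none to reproduce. The check is date arithmetic plus the bias of a before/after comparison under a linear trend.

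**Inputs.** Cut 11 March 2020 (WP 2.1). First wave 1 February to 30 June 2020 (Section 4, WP 2.2). Cohorts 1.1.2015 to 31.12.2022 for NSCLC and OSCC, and 1.1.2012 to 31.12.2022 for MIBC (WP 1.1). Outcome window six months (WP 2.1). Assumed: uniform accrual. Pre-COVID time is 1,896 days (NSCLC, OSCC) or 2,992 days (MIBC); post-COVID time is 1,026 days.

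**1. Date conflict.** 1 February to 10 March 2020 is 39 days, out of a 151-day first wave. Share of pre-COVID time: 39/1,896 = 2.1%; MIBC 39/2,992 = 1.3%.

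**2. Windows crossing the cut.** Diagnoses from 11 September 2019 to 10 March 2020 span 182 days: 182/1,896 = 9.6%; MIBC 182/2,992 = 6.1%. These are upper limits. With an assumed mean time to treatment of 30 to 90 days, the share treated after the cut is about 30/1,896 to 90/1,896 = 1.6% to 4.7%; MIBC 1.0% to 3.0%. If the first-wave exclusion is applied by diagnosis date, 182 − 39 = 143 such days remain: 143/1,857 = 7.7% of the remaining pre-COVID time; MIBC 143/2,953 = 4.8%.

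**3. Trend.** Spurious difference = slope × distance between period midpoints. Distance = (1,896 + 1,026)/2 ÷ 365.25 = 4.0 years; MIBC (2,992 + 1,026)/2 ÷ 365.25 = 5.5 years. No slope is given, so a range is assumed:

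| Assumed trend (points/year) | NSCLC, OSCC (points) | MIBC (points) |
|---|---|---|
| 0.25 | 1.0 | 1.4 |
| 0.5 | 2.0 | 2.75 |
| 1 | 4.0 | 5.5 |
| 2 | 8.0 | 11.0 |

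These are on the probability scale; the planned model works on the logit scale. Removing the first wave moves the midpoints to 4.2 and 5.7 years apart, so that analysis slightly enlarges a trend bias.

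**4. Precision cost of a trend term.** With a share c of accrual before the cut, the squared correlation between the COVID indicator and linear time is 3c(1−c), so the variance inflation is 1/(1−3c(1−c)).
- NSCLC, OSCC: c = 1,896/2,922 = 0.649; inflation 3.2; standard error × 1.8.
- MIBC: c = 2,992/4,018 = 0.745; inflation 2.3; standard error × 1.5.
- With a change in level and slope, the variance of the level change goes from 1/n₁ + 1/n₂ to 4/n₁ + 4/n₂, where n₁ and n₂ are the numbers before and after the cut; standard error × 2.

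**The case against.** The best defence has four parts.

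- **The compared groups do not overlap.** A reader might infer from the two dates that some patients are counted in both arms of the contrast. They are not: WP2 splits once, at 11 March 2020. The conflict is between that cut and the first-wave definition, and the sensitivity analysis removes the 39 days. This stands; the dates still need reconciling.
- **The crossing windows are a small, mainly diluting problem.** This also stands. They do not move underlying change into the COVID effect. WP 2.2 also does not say whether the first-wave exclusion works by diagnosis or treatment date.
- **Time period may be finer than a two-level block.** Each model adjusts for it, and the first assessment concerns inequalities before COVID. If that model is fitted to pre-COVID patients only, a pre/COVID indicator would be constant. The SAP, not seen here, or the WP2 protocol listed in WP 1.7 may specify a trend. This stands as far as it goes, so trend bias is a conditional risk. Against it, Section 4 and the WP2 overview use the phrase for blocks before and during the pandemic, and no trend-by-group term is named.
- **Delay past six months is arguably part of COVID's impact.** A reader might infer that counting late curative treatment as non-curative is a plain error. The protocol does not support that: the six-month rule defines the outcome, and WP 2.1 will describe variation in time to treatment. What remains is that the modelled outcome cannot tell delay from non-receipt, and the nine-month cut-off is listed only in WP 3.4.

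**Conclusion.** The concern holds in a limited form.

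- The date conflict is a matter of fact: 39 days, 2.1% of pre-COVID time (MIBC 1.3%).
- Contamination of the reference follows from the stated definitions, is bounded at 9.6% (MIBC 6.1%), is probably smaller, and would mostly weaken the contrast.
- The trend issue is potentially the largest but is conditional. It needs time period to mean the pre/COVID block and a real trend to exist; for changes in inequality, the trend must differ between groups. Its size rests on uniform accrual and on a slope the protocol does not give.

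A reader might conclude that the plan does attribute secular change to COVID. The text does not establish that. It leaves the possibility open, and the one planned check on pandemic timing, excluding the first wave, cannot detect it. The quarterly patient numbers in WP 2.2 are descriptive and do not correct the modelled contrast.

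**What to change.** 1. Use one COVID start date in Section 4, WP2 and WP3, and say whether the first-wave exclusion works by diagnosis or treatment date.
2. Keep diagnoses whose six-month window crosses that date out of the pre-COVID reference, as a transition group or at least in a sensitivity analysis.
3. Define the time-period term. Fit the COVID contrast with a calendar-quarter trend and its interaction with the sociodemographic factor under study, and report it beside the simple before/after contrast.
4. Repeat WP2 with the nine-month window from WP 3.4 as a sensitivity analysis that separates delay from non-receipt, lengthening the transition group to match.

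The cost in work is low: wording, extra model terms and one more run on data the study already plans to use. The reference group shrinks slightly, by no more than the crossing-window share. The loss of precision is not slight. Given the standard-error multipliers above (1.8 or 1.5 with a linear trend, about 2 with a change in level and slope), subgroup results for OSCC, with about 5,000 patients, will be imprecise. This is why both contrasts should be shown.

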Secondary outcomes will include: all-cause and cancer-specific mortality at 30 days, 90 days, 12 months, and 24 months, time to death, and the number of days in hospital prior to 12 months, as this may be associated with grade three or four adverse events. We will use life tables in England according to calendar year, region, age, gender, deprivation and ethnicity to calculate rates of net cancer survival, which recognise the excess risks of death following a cancer diagnosis, versus those for the general population [66].

Effect size	Standard	_	Levels c	of compliance (IV	strength):
(three-year mortality difference in level of absolute risk)	deviation of the outcome in the population	Proportion of patients receiving RT	0.5	0.6	0.7
5%	0.3	0.5	4,521	3,140	2,307
5%	0.4	0.5	8,037	5,581	4,101
5%	0.4	0.6	8,372	5,814	4,271
10%	0.3	0.5	1,130	785	577
10%	0.4	0.5	2,009	1,395	1,025
10%	0.4	0.6	2,093	1,453	1,068

Table 3: Required sample size (N) for the IV design according to instrument strength(level of compliance) and magnitude of effect size at 80% power

WP 3.2 Quantitative analysis of the target trials (leads [name], [name], advisor [name] developer of the local instrumental variable method)

The analysis will recognise that even after applying the target trial inclusion criteria, and adjusting for measured covariates, the choice of curative RT versus surgical treatment will reflect some organisational (e.g. MDT composition) or patient factors (e.g. patient preference) that are not available within the linked data. We will use the instrumental variable approach taken in the ESORT study to address this form of confounding by indication due to unmeasured factors that commonly arises with routine data (52-54,64).

The instrumental variable approach will be set out in a Statistical Analysis Plan. In brief, we will draw from previous research that has used distance or travel time, as an instrumental variable for treatment choice (67). Recent work by co-applicant [name] found that travel time to the nearest RT centre from a patient's area of residence predicted whether they had curative RT or surgery (41). Our PPI colleagues have emphasised that increased travel time may discourage patients from having curative RT versus surgery as this requires more outpatient visits. We will calculate a continuous measure of travel time from the patient's area of residence to the nearest NHS trust that provides curative RT (see WP1). We will use this measure of travel time as an instrumental variable for the receipt of curative RT versus surgery. This instrumental variable will be combined with adjustment for measured covariates to minimise bias from unobserved confounding in comparing 3-year mortality following curative RT versus surgery, for eligible patients with each of these three early-stage cancers.

Box 1: Results from Pilot work supporting the Instrumental Variable approach

We undertook *preparatory work* using the 2014-17 national linked cancer data for early stage OSCC which has the smallest sample size across the 3 conditions, and hence presents a greater challenge for the instrumental variable approach. We found that the essential assumptions for travel time to be an instrumental variable were realistic. *First*, the travel time from the patients' area of residence to the nearest NHS trust providing curative RT was associated with receipt of curative RT versus surgery (F statistics >20 versus the recommended cut-off of >10). *Second*, travel time balanced prognostic measures such as the patients' cancer stage. We will repeat these assessments on the final linked data for all three conditions, which given the larger sample sizes would be anticipated to yield a stronger instrument. The assumption that travel time is independent of unmeasured confounders cannot be assessed empirically, but is likely to be justified, since after accounting for measured baseline variables (geographical place of residence, deprivation level, time period, 'centre' and other quality of care variables), it is unlikely that travel time direct predicts all-cause mortality. This assumption will also be discussed with the clinical panels (W1) (see also sensitivity analyses).

WP 3.3 Estimating effectiveness of curative RT versus surgery for each tumour type

The three target trials will report differences between the comparison groups according to absolute risk differences for three-year mortality (primary endpoint) and other binary measures, and difference in means for continuous measures (secondary endpoints). We will use a local instrumental variable approach to estimate the relative effectiveness of RT versus surgery for each individual, as this approach can fully account for confounding and heterogeneity across patient subgroups (54). We will report relative effectiveness across all patients included in each target trial, and for each pre-specified subgroup of interest: tumour size and spread to nearby lymph nodes and/or to distant sites, age (years), performance status, smoking status, Charlson comorbidity index, and year of diagnosis. This analysis will

be conducted according to the intention-to-treat principle, recognising that patients may experience delays in the receipt of either curative intervention, may not complete their allocated treatment or may switch from one treatment option to the other. Following this principle, we will include all patients from the time they meet the inclusion criteria, and adjust for covariates anticipated to predict the assigned treatment and the outcome, according to their observed level at baseline (time zero).

The local instrumental variable approach comprises two stages. In the first stage, Probit regression models will be used to estimate the initial propensity score as a function of covariates and the IV. In the second stage, this predicted propensity score will be included alongside covariates in Generalised Linear Models with appropriate link functions for continuous or binary outcomes. Models at both stages will adjust for case-mix, organisational-and temporal factors described above including time period, proxies for care quality, defined by rates of 30-day and 1-year mortality for each NHS hospital trust for the early-stage cancers in question, for the year prior to the individual's diagnosis. The estimates will be reported with bootstrapped confidence intervals that allow for the clustering of individuals within NHS trusts and cancer alliances, and with multiple imputation to allow for missing covariate information.

WP 3.4 Sensitivity analyses

Sensitivity analyses will be undertaken to assess whether the results are robust to alternative definitions and assumptions. First, alternative inclusion criteria with respect to the time to curative treatment will be applied, including stricter (within three months of diagnosis), and looser (within nine month) cut-offs. Second, we will consider as an alternative instrumental variable, the percentage of eligible patients receiving RT versus surgery in each NHS trust in the year preceding the individual patient's diagnosis. Third, rather than using an instrumental variable analysis, the study will instead undertake conventional risk adjustment assuming that all relevant confounders have been measured, while assessing the impact of plausible levels of unobserved confounding on the results. Fourth, as in WP2, we will exclude data from the first wave of COVID-19 in England to assess the extent to which the results are sensitive to the inclusion of this period that is anticipated to be atypical for the provision of cancer services.

WP 3.5 Output and Interpretation of results (leads [name], [name], [name], [name], [name], [name])

We will report the relative effectiveness of RT versus surgery according to differences in absolute risk of 3-year mortality for each cancer. In interpreting the results, we will draw on insights from the clinical panels, and patient interviews, about the influence of local organisational factors and patient preferences on curative treatment decisions. The interpretation of the results will be according to the specific time-period. This will be important to provide recommendations for periods when the NHS is under exceptional pressures, such as during the first wave of COVID-19, and under prolonged pressures; for example, the increasing waiting lists for cancer care during the subsequent waves of COVID-19.

WP 4: Cost-effectiveness (Objective 4) (lead [name] and [name] advisor on combining inequality and costeffectiveness)

The cost-effectiveness analyses (CEA) will take the NHS and Personal Social Services perspective recommended by NICE. For each early-stage cancer we will report the relative cost-effectiveness of curative RT versus surgery strategies, over a lifetime time horizon. The choice of comparators will not include a 'no curative treatment alternative' as this is not a recommended treatment alternative for people with these early-stage cancers. The study will

incorporate patient-level resource use and mortality data from the linked dataset, combined with unit costs and health-related quality of life (HRQoL) estimates from the literature (68-73). The CEA will follow the assessment of effectiveness, in using travel time as an instrumental variable to address confounding. The value of implementation analysis will incorporate the findings about inequalities (WP1), to report the value of increasing the uptake of the most cost-effective curative intervention for each cancer, within sociodemographic groups (e.g. according to deprivation-level).

WP 4.1 Resource use and unit costs

The linked datasets will identify resource use data for those categories anticipated to drive incremental costs, including the delivery of radiotherapy, surgical treatments, systemic care, hospital inpatient stays, and outpatient visits. Data for all types of external beam radiotherapy, doses, and fractions delivered to eligible patients will be extracted. We will identify the OPCS code of all surgeries and operative procedures performed on each eligible patient. We will obtain the drug administered, dose, number of cycles, and route of administration for patients undergoing chemotherapy including pre- or perioperative therapies, as well as those with curative and palliative intent. Information from the linked dataset on all hospitalisations since the date of cancer diagnosis will be extracted. We will distinguish between the time spent in critical care and on general wards, and all outpatient visits and accompanying medical procedures (e.g. imaging),

Unit costs, including those for RT and surgical strategies, will be taken from the NHS National Costs Collection (74) and the PSSRU Unit Cost databases (75). We will combine resource use with unit costs to report total costs per patient for the maximum duration of follow-up.

Outcomes

We will use ONS data for vital status which will be available for between three and seven years from date of diagnosis. We will calculate the number of life year years from the date of diagnosis up to three years, and for the maximum observation period available. We will use the maximum available survival data in extrapolations to lifetime survival, recognising that for these three tumour types 5-year survival is relatively low. These extrapolations will follow recent recommendations (76), and in choosing the more appropriate parametric models will differentiate between mortality that is 'cancer-specific' (see WP3), versus 'background' all-cause death for which general population death rates will be more appropriate.

We have undertaken a literature review of published studies that used a recommended, generic instrument to estimate HRQoL for these early-stage cancer patients (68-73). HRQoL estimates for each cancer, and according to disease stage, performance status, age, and number of comorbidities will be extracted from the sources selected. We will use the 'area under the curve' approach, to combine survival time with HRQoL estimates from the literature review, to report lifetime quality-adjusted life years (QALYs) for each cancer.

WP 4.2 Evaluating relative cost-effectiveness of RT versus surgery

We will extend the previous instrumental variable analyses to report the incremental net monetary benefit (INB) of curative RT versus surgical strategies overall and for those subgroups for whom there is a clinical and decision-making rationale (e.g. cancer stage, performance status)

WP 4.3 Sensitivity analyses

We will re-consider the previous scenarios (WP3) for the CEA. In addition, we will consider alternative time horizons (five years versus lifetime), different parametric models for the extrapolations, and alternative sources of HRQoL data. Finally, we will adopt a societal perspective by incorporating patient costs e.g. travel time, or time away from usual activities while receiving or recovering from either curation intervention.

WP 4.3 Evaluating the value of implementation (advisor [name], York)

The study will combine the findings from the inequalities research (WP2) with those of the CEA (WP4). While we considered using a distributional cost-effectiveness framework, it was judged impractical to apply within this study. In particular, the requisite weights to address any 'efficiency versus equity trade-offs' were not available, and eliciting appropriate weights within the proposed research was judged infeasible. Instead, we will apply a value of implementation framework (77) to combine the inequalities (WP2) with the CEA results. For each underserved subgroup, we will estimate the value and costs of increasing the uptake of the more cost-effective intervention, from current levels to 100%. We will identify the number of patients in each sociodemographic subgroup who either receive no curative treatment or the less cost-effective intervention. We will consider the expected effectiveness and costs of specific implementation strategies. We will draw on insights from the clinical panels and patient interviews in considering barriers that subgroups may experience in accessing curative treatments within complex cancer pathways.

WP 4.4 Output: we will provide evidence about which curative intervention is most costeffective for each early-stage cancer. We will provide evidence to help service providers improve uptake of the curative intervention that is more cost-effective overall, with a focus on those sociodemographic subgroups for whom uptake is relatively low.

6. Dissemination, knowledge mobilisation and pathways to impact

